12.2. Concomitant Medications

Listing 16.2.6 entitled *Concomitant Medications* will be presented by subject and include all of the information recoded on the concomitant medication form. This listing will be sorted by

November 7, 2018

subject number and the name of the concomitant medication; the date may not be complete for all patients and medications and may not be used as an index variable for sorting.

Listing 16.2.6.1 entitled *Analgesic Medications* will be presented by subject and include all of the information recoded on the concomitant medication form for analgesic medications taken for DSPN. This listing will be sorted by subject number and the name of the analgesic medication; the date may not be complete for all patients and medications and may not be used as an index variable for sorting.

Total dose by patient will be summarized and reported in Table 14.1.13 entitled *Summary of the Dose of Analgesic Medication Taken for DSPN by Randomized Treatment Assignment and Time*. Total rescue medication dose by patient will be summarized and reported in Table 14.1.14 entitled *Summary of the Dose of Rescue Medication by Randomized Treatment Assignment and Time*.

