neuropathic pain score of ≥ 4 and ≤ 9 (calculated as the average of the last 7 days preceding the enrollment visit), and review of stable analgesic pain consumption profile during the 14-day runin period. Qualified subjects based on diary compliance and average pain score will be randomized 1:1 (active: sham) and will be instructed to self-treat twice daily (morning and evening; 8am \pm 2 hours and 8pm \pm 2 hours) for 120 days. Subjects will record electronic patient-reported outcome (ePRO) data following each morning treatment for 120 days. Subjects consenting to distal thigh and distal leg skin biopsies during the Screening visit will have biopsies collected and sent to the central laboratory for assessment. All subjects will have a baseline Skin Perfusion Pressure (SPP), Sural Nerve Conduction Studies (NCS), Quantitative Sensory Testing (QST), and will complete the Work Productivity and Activity Impairment Questionnaire (WPAIQ), and NeuroOoL.

Subjects will receive a telephone call at Day 7 to ensure compliance to treatment and diary completion, provide followup information on the biopsy sites (if applicable), complete a blinding assessment as well as be assessed for safety and concomitant medication changes.

At **Month 1** subjects will return to the clinic for evaluation of safety, concomitant medication changes, review device usage (reports will be supplied to the site) and ePRO diary completion, and Patient Global Impression (PGI). Treatment satisfaction will also be assessed.

At **Month 2** subjects will return to the clinic for evaluation of safety, concomitant medication changes, treatment satisfaction, review of device usage (reports will be supplied to the site) and ePRO diary completion, quality of life outcomes (WPAIQ and NeuroQoL), Patient Global Impression (PGI), and interim visit measurements of SPP.

At **Month 3**, subjects will return to the clinic for evaluation of safety, concomitant medication changes, review device usage (reports will be supplied to the site) and ePRO diary completion, and Patient Global Impression (PGI). Treatment satisfaction will also be assessed.

At **Month 4** (end of Part A / start of Part B), subjects will return to the clinic for evaluation of safety, treatment satisfaction, review of device usage (reports will be supplied to the site), HbA1c, concomitant medication changes, weight, quality of life

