4.1 Visit 1 – Screening Visit (Day -15)

The Screening Visit will take place 15 days prior to the Enrollment Visit. If a successfully screened subject falls more than 1 day early (earlier than day -14) or more than 2 days late (later than day -17), the subject will require another screening and run-in period to

participate in the trial. The following procedures will be performed during the Screening Visit:

- 1. Informed consent review and signature
- 2. Review Inclusion and Exclusion criteria
- 3. Collect Toronto Clinical Neuropathy Scoring System for Inclusion
- 4. Obtain baseline pain score (baseline score must be \geq 4 and <9 for eligibility)
- 5. Collect subject demographic data (including age, weight, height, gender, race/ethnicity)
- 6. Collect baseline diabetes related health resource utilization including the regimen for their diabetic care (number of doctors' visits and history of ulcers)
- 7. Collect Medical and Surgical History
- 8. Collect depth, width, and length foot measurements and shoe size for each foot
- 9. Conduct directed physical exam (abnormal or normal) for General Appearance, Cardiovascular, Musculoskeletal, Extremities/Skin, Neurological, and Other
- 10. Obtain Ankle-Brachial Index
- 11. Assess venous insufficiency
- 12. Measure HbA1c
- 13. Review and record medications taken for their diabetic neuropathy pain (including over the counter PRN)
- 14. Review and record all additional medications
- 15. Perform a urine pregnancy test for females of child bearing potential
- 16. If the subject meets the eligibility criteria, enroll the subject in to the 14-day ePRO run in period in the ePRO system.

During this visit, the subject will be introduced to the electronic (ePRO) diary and trained in the proper use of the patient-reported-outcome (PRO) assessment tools for pain intensity and analgesic consumption for their diabetic neuropathy pain (including over the counter and prn medications). Analgesic medications taken for their diabetic neuropathy pain will be captured in the ePRO and subjects will enter the number of pills they have taken over the last 24 hours. The ePRO diary can be accessed by the subject through any device that has an internet connection and web browser.

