Subjects will be instructed to utilize their prn analgesic medications prescribed prior to enrollment in the event their diabetic neuropathy pain increases during the trial, and not to introduce new medications or therapies into their analgesic treatment regimen through Month 6 (Day 180) of the trial. In this context, "analgesic medications" includes but is not limited to nonsteroidal anti-inflammatory agents, anti-depressants and muscle relaxants, and includes medications taken on an "as needed" (prn) basis (including over the counter medications) as well as those medications taken on a regular schedule.

4.2 14-Day Run-In Period

The subject will be instructed to record NPRS scores at 8 am (\pm 2 hours) for 14 consecutive days beginning the day following the Screening Visit. There will be 2 questions generated on a daily basis, one question will address diabetic neuropathy pain and a separate question will ask the subject to enter consumption (number of pills/tablets/capsules) of each indicated analgesic taken for their neuropathic pain over the previous 24 hours.

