7.2. Handling of Dropouts or Missing Data

Missing data may have an impact upon the interpretation of the trial data. Values for missing data will not be imputed, however a methodology is defined for missing dates. All available data for subjects who do not complete the study will be included in the data listings. An analysis of the last recorded observation will be conducted to facilitate a comparison predicated on the ITT population.

Safety Data

Missing or incomplete data will not be imputed. For patients who withdraw from the study prematurely, the last recorded observation will serve as final observation.

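### SAP 12.2 summarises analgesic and rescue use as total dose per patient with no denominator, so missed diary days can read as lower drug use

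*SAP*

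**What the plan says.** SAP 12.2 plans two summary tables. For analgesics taken for neuropathy: "Total dose by patient will be summarized and reported in Table 14.1.13". For rescue use: "Total rescue medication dose by patient will be summarized and reported in Table 14.1.14". The title of that second table is "Summary of the Dose of Rescue Medication by Randomized Treatment Assignment and Time"; Table 14.1.13 is likewise split by arm and time. The section does not divide by days, give the length of a time interval, or say what happens to an unanswered diary day or after withdrawal. No test or model is attached to either table.

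The source of the totals is not stated. The listing described just before them, Listing 16.2.6.1, is to "include all of the information recoded on the concomitant medication form for analgesic medications taken for DSPN". The protocol collects the counts another way. In Protocol 4.1, "subjects will enter the number of pills they have taken over the last 24 hours". In Protocol 4.2, for the run-in, "a separate question will ask the subject to enter consumption (number of pills/tablets/capsules) of each indicated analgesic taken for their neuropathic pain over the previous" (the recall period is again one day). For the treatment period the synopsis says: "Subjects will record electronic patient-reported outcome (ePRO) data following each morning treatment for 120 days". Protocol 4.19 confirms daily pill counts in the ePRO system through 120 days and sends analgesics taken for other reasons to the chart.

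On missing data, SAP 7.2 states: "Values for missing data will not be imputed". Its safety paragraph takes the last recorded observation as final for patients who withdraw, which has no clear meaning for a cumulative dose. SAP 4.4 says that nothing more is collected after withdrawal. For the pain score from the same diary, Protocol 7.1 does give a missed-day rule: a weekly mean needs at least 3 recorded days.

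**The concern.** A sum of recorded pills mixes three things: how much the patient takes per day, what share of days the diary is answered, and how long the interval is. Only the first is of interest. Because recall covers 24 hours, the next entry does not recover a missed day. Because nothing is imputed, an unanswered day adds nothing to the sum. This would be so even with a single drug, so it is separate from the question of adding unlike drugs together.

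Protocol 4.1 tells subjects to turn to their existing prn analgesics if pain increases, and the primary model in SAP 11 has no term for analgesic use. The question of whether a difference in NPRS could reflect medication therefore falls to these two tables. On a total, an arm that answers fewer diaries could appear to need less medication, and real extra use could disappear.

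**Working it through.** The documents give no figure for medication use, so there is none to reproduce. The check is arithmetic:

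recorded total = true daily use × days in the interval × share of days answered.

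**From the documents:** 14-day run-in (Protocol 4.2); visits at Days 30, 60, 90 and 121, each ±3 days (Protocol Appendix A); 120 diary days (synopsis); 30% premature discontinuation (Protocol 7.4).

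**Assumed:** true use of 1 pill per day in both arms unless stated; diary completion between 70% and 100%; patients who leave do so at Day 60 on average; totals built from the diary.

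**1. Missed days**

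| Completion | 30-day total | 120-day total |
|---|---|---|
| 100% | 30 | 120 |
| 90% | 27 | 108 |
| 75% | 22.5 | 90 |
| 70% | 21 | 84 |

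With 75% in one arm and 90% in the other, 22.5 / 27 = 0.833, an apparent 17% reduction at equal use. With 70% against 90%, 21 / 27 = 0.778, or 22%. With equal completion the relative difference is zero.

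**2. Masking.** 1.2 pills per day at 75% completion: 1.2 × 30 × 0.75 = 27. 1.0 pill per day at 90%: 1.0 × 30 × 0.90 = 27. A 20% higher true use leaves no trace.

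**3. Interval length.** If a 14-day run-in total is set against a 30-day total, constant use gives 30 / 14 = 2.14. The visit windows also let a nominal 30-day interval run from 24 days (Day 33 to Day 57) to 36 days (Day 27 to Day 63). Intervals of equal length, such as weeks, would remove both effects.

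**4. Dropout, under two readings**

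- One 120-day total, full diaries: arm mean = 120 × (1 − d) + 60 × d. For d = 10%, 20% and 30% this gives 114, 108 and 102. At 30% the understatement is 1 − 102 / 120 = 15%. Between arms, 30% against 20% gives 102 / 108, or −5.6%; 30% against 10% gives 102 / 114, or −10.5%.
- Totals by interval, withdrawn patients absent afterwards: only the interval of withdrawal is short. If withdrawn patients are entered as zero, the first result returns.

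**5. Use per answered day.** Pills recorded divided by days answered returns 1.0 per day in both arms in every equal-use case above, and 1.2 against 1.0 in step 2.

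**The case against.** A reader might infer that dropout as such will count as lower drug use. The documents do not support that. Both tables are split by time, and the SAP's display for repeated measurements (Level 3, SAP 7) leaves out patients without the later visit and does not score them zero. The SAP does not say that the dose tables use Level 3, but nothing says that withdrawn patients count as zero. On the by-time reading, dropout affects only the interval in which the patient leaves.

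A reader might also put the 15% dropout figure beside the 2.1-fold rise. They belong to different tables: the first needs one 120-day total, the second separate and unequal intervals. Nor is 15% firmly anchored. The 30% stands in Protocol 7.4 only, while SAP 4.3 describes the same 162 as 1.3 times 124, which absorbs a loss of 1 − 1/1.3 = 23% and would give about 11.5%. The 70% diary figure is an entry floor for the run-in, so it does not predict a 30% understatement on treatment.

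The data source is a fair challenge. SAP 12.2 names the concomitant medication form for the listing and no source for the tables. The diary remains the likelier source: the protocol puts daily pill counts there, and SAP 12.2 itself warns that dates on the form may be incomplete, a poor basis for a dose by time. That is an inference all the same.

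The stakes are also limited. Analgesic use is not among the 11 endpoints in SAP 3.1.1, the tables carry no test, and Listing 16.2.6.1 shows analgesic data by subject. Prn use is bounded too, since Protocol 4.19 bars changes to the pain regimen. All of this stands. It reduces the point to the choice of measure in two descriptive tables, but does not make a total without a denominator a sound one.

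**Conclusion.** The point holds as a weakness in how two tables are defined. If the totals are built from the diary, missed days lower recorded use under any reading of the time split. The size is about 17% for 75% against 90% completion, enough to hide 20% higher true use. Those completion rates are assumptions. The plan states no diary minimum on treatment, and the per-protocol set is defined by device use. Distortion between arms requires completion to differ by arm and can run in either direction. Dropout adds to it only for a whole-period total, for withdrawn patients set to zero, or within the interval of withdrawal. The 2.1-fold rise over baseline applies only if unequal intervals are used.

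A reader might take the tables as a formal comparison of the arms; they are not. Their weight comes from being the only by-arm summaries of analgesic use described in the SAP text (the separate table index cited in SAP 15 is not part of these documents). The primary analysis, its error rate and the sample size are unaffected.

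**What to change.** In SAP 12.2, for Tables 14.1.13 and 14.1.14:

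- Replace total dose with mean daily use: pills or dose summed over diary days on which the analgesic question was answered, divided by the number of those days, per patient and period.
- Use run-in mean daily use as the baseline.
- Show the number of answered days by arm and period.
- Name the ePRO diary as the source and define the periods.
- State that withdrawn patients are absent, not zero, in intervals after withdrawal.

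A minimum number of answered days, such as the 3 per week used for the pain score, is optional: the ratio does not need it, and it discards data.

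The cost is SAP wording and a changed derivation in two tables, with no new data. The downside is that the mean treats unanswered days as like answered ones. That is weaker than treating them as days without medication, but patients may skip the diary on days when use is unusual. The change does not correct for dropout that is related to pain or drug use.

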12.3. Additional Tabulations

The following additional tables will be generated.

	Summary of the Blinding Assessment by Randomized Treatment Assignment and
14.4.1.9	Time
	Summary of the Toronto Clinical Neurpathy Scoring System by Randomized
14.4.1.10	Treatment Assignment and Time
14.4.1.11	Summary of HbA1c by Randomized Treatment Assignment and Time
	Summary of the Treatment the Subjects Believe they are Receiving by Randomized
14.4.1.12	Treatment Assignment and Time

13. PROGRAMMING SPECIFICATIONS FOR STATISTICAL ANALYSES AND SUMMARY TABLES

13.1. Summary tables

- All tables and data listings will be presented in Landscape Orientation, unless presented as part of the text in a CSR.
- Figures will be presented in Landscape Orientation.
- Legends will be used for all figures with more than one variable or item displayed.
- Figures will be in black and white. Symbols on figures will not be filled. Lines should be wide enough to see the line after being copied.
- Specialized text styles, such as bolding, italics, borders, shading, superscripted and subscripted text will not be used in tables, figures, and data listings unless they add significant value to the table, figure, or data listing.
- Only standard keyboard characters should be used in tables and data listings. Special characters, such as non-printable control characters, printer specific, or font specific characters, will not be used on a table, figure, or data listing. Hexadecimal character representations are allowed (e.g., μ , α , β).
- All titles will be centered on a page. The first title line will be the number of the table, figure, or data listing. The second (and if required, third) line will be the description of the table, figure, or data listing.
- All footnotes will be left justified at the bottom of a page. Footnotes must be present on the page where they are first referenced. Footnotes should be used sparingly and must add value to the table, figure, or data listing. If more than four footnote lines are planned then a cover page may be used to display footnotes.
- Missing values for both numeric and character variables will be presented as blanks in a table or data listing.
- All date values will be presented as DDMMMYYYY (e.g., 29AUG2013) format. A four-digit year is preferred for all dates.
- All observed time values will be presented using a 24-hour clock HH:MM:SS format (e.g., 01:35:45 or 11:26). Seconds should only be reported if they were measured as part of the study.
- Time durations will be reported in mixed HHhr MMm SSs notation (e.g., 5h 32m, or 27h 52m 31s). The use of decimal notation to present time durations should be avoided (e.g. 0.083h = 5m) unless it is necessary to show the computation of time differences in a table, figure, or data listing, in which case both notations may be used to display the time duration.
- All tables, figure, and data listings will have the name of the program and a date/time stamp on the bottom of each output.
- Population sizes may be presented for each treatment or dosing category as totals in the column header as (N=xxxx), where appropriate.
- Population sizes shown with summary statistics are the samples sizes (n) of patients with non-missing values.
- All population summaries for categorical variables will include categories that the patients had a response in these categories.
- All percentages are rounded and reported to a single decimal point (xx.x%).

November 7, 2018

• Population summaries that include p-values will report the p-value to three decimal places with a leading zero (0.001). All p-values reported on default output from statistical software (i.e., SAS® Software) may be reported at the default level of precision. P-values <0.001 should be reported as <0.001 not 0.000.

13.2. SAS Code for Generic Statistical Procedures

Note: Not all procedures may be required for the presentation of the results from this study. Information provided for procedures not directly referenced in this SAP may be used in supportive analyses.

1) SAS code for Kaplan-Meier analyses

```
PROC LIFETEST PLOT=(S) DATA = thedataset;
TIME DAY*CENS(1);
STRATA group;
```

CENS: Censoring variable: CENS=1 if censored, 0 otherwise.

DAYS: Time to event or censoring. group: group to test for differences.

Note: Survival probabilities are determined from the SURVIVAL variable in the PRODUCTLIMITESTIMATES ODS data set. Survival probabilities are determined at the observed values of the time variable. Survival probabilities at other days can be determined as the last survival probability up to the specified day.

2) SAS code for Cox analyses

Dummy variables must be constructed for center and treatment. If there are C centers, construct C-1 dummy variables as

```
CENTER_2 = (CENTER = second center number); ...

CENTER_C = (CENTER=last center number);
```

Note that one arbitrarily chosen center is not accorded a dummy variable.

For treatment, construct a dummy variable XXX treatment groups:

```
XXX = (TREAT = "XXX");
```

The control group is not accorded a dummy variable. Note: the coding of interactions must be determined.

The SAS code for the full model is then (replacing ... with full list of variables):

```
PROC PHREG DATA=input-data-set;
MODEL DAY*CENS(1) = TREATMENT CENTER_2 ... CENTER_C BASELINE;
OVERALL CENTER: TEST CENTER 2,..., CENTER C;
```

CENS: Censoring variable: CENS=1 if censored, 0 otherwise. The observation will be censored if the patient finishes the study or discontinues without responding.

Regenesis Biomedical, Inc. Protocol RBI.2017.002 Statistical Analysis Plan

Analysis Plan November 7, 2018

DAY: Time to event or censoring. CSTRATUM: Study center (stratum).

TREAT: Treatment.

Note: Survival probabilities are determined from the SURVIVAL variable in the output file. Survival probabilities are determined at the observed values of the DAY variable. Survival probabilities at unobserved days can be determined as the last survival probability at the observed day before the desired day. In this study it is likely (but not certain) that the median times will occur on an observed day.

Calculation of confidence intervals for the hazard ratio

The 95% confidence interval on the hazard ratio is calculated with the following formula:

(exp(estimate-SE*1.96), exp(estimate+SE*1.96)).

3) SAS (version 9.2) code for the ANOVA models for analyzing efficacy parameters

PROC GLM DATA=inputdataset;

CLASS TREATMENT CENTER;

MODEL variable = TREATMENT CENTER BASELINE;

** differences with CONTROL;

ESTIMATE "ACTIVE-CONTROL" TREATMENT -1 1 / cl alpha=.05;

The values are obtained from ODS data sets as shown in the next table:

Statistical Quantity	ODS Data Set	Record Identifier in ODS	Variable
Estimates by treatment	LSMEANS	TREAT=1 etc.	LSMEAN
Estimates of treatment difference	ESTIMATES	LABEL='TREATMENT- CONTROL'	ESTIMATE
CI on treatment difference	ESTIMATES	LABEL='TREATMENT- CONTROL'	LOWER, UPPER
P-value for treatment difference	ESTIMATES	LABEL='TREATMENT - CONTROL'	PROBT

For subgroup analyses including a discrete covariate such as gender, include the term as follows:

PROC GLM DATA=inputdataset;

CLASS TREATMENT CENTER GENDER;

MODEL variable = TREATMENT CENTER GENDER BASELINE;

PROC GLM DATA=inputdataset;

CLASS TREATMENT CENTER GENDER;

MODEL variable = TREATMENT CENTER GENDER TREATMENT*GENDER BASELINE;

4) SAS (version 9.2) code for the confidence intervals on means

PROC UNIVARIATE DATA=inputdataset CIBASIC; VAR value;

where VALUE is the analysis variable. Confidence intervals are obtained from the BASICINTERVALS ODS data set. The confidence interval is from the LOWERCL and UPPERCL variables on the record where UPCASE(VARNAME) EQ 'MEAN'.

5) SAS code for analyses using PROC FREQ

PROC FREQ DATA = thedataset; TABLES response*group / CHISQ;

The p-value comparing GROUPs is taken from the PROB variable in the ODS EXACT dataset. The record for the Fisher's exact test is the record for which UPCASE(STATISTIC) EQ "FISHER".

6) SAS code for CMH analyses

PROC FREQ DATA = the dataset; TABLES strata*treatment*response / CMH;

The following table shows the sources of the values obtained from the Output Delivery System data sets.

Statistical Quantity	ODS Data Set	Record Identifier in ODS	Variable
P-value for treatment	СМН	UPCASE(ALTHYPOTHESIS) =ROW MEAN SCORES DIFFER	PROBF

where RESPONSE is the variable being analyzed, and strata is the variable being controlled for (e.g., CENTER).

7) SAS code for Cochran-Mantel-Haenszel (CMH) analyses with ordered response (Van Elteren test)

PROC FREQ DATA = thedataset;

TABLES strata* treatment*response / CMH SCORES=MODRIDIT;

8) SAS code for 2-sample Wilcoxon test

PROC NPAR1WAY WILCOXON DATA=inputdataset;

CLASS TREATMENT;

VAR analysis_variable;

Statistical Quantity	ODS Data Set	Record Identifier in ODS	Variable
P-value for treatment difference	WILCOXONTEST	(UPCASE(LABEL1) EQ "TWO- SIDED PR > Z) AND UPCASE(NAME1) EQ "PT2_WIL"	NVALUE1

